6.9.2.3. Exploratory Pharmacodynamic Analyses

The retrospective VAS, FCI, and FPQ questionnaires parameters are added below for exploratory analyses:

Retrospective VAS

Exploratory PD measures to assess the effect of tirzepatide 15 mg versus placebo for change from baseline through Week 18 in retrospective VAS (collected 16 times) subscores and overall score:

- subscores:
 - o hunger
 - o fullness
 - o satiety
 - o prospective food consumption
- overall score

Note: The retrospective VAS (Womble et al. 2003) will be used to measure the average ratings of appetite that subjects experienced over the past week. The questionnaire consists of only 4 questions, which correspond to 4 appetite subscales (hunger, satiety, fullness, and prospective food consumption). Overall appetite score is calculated as the average of the 4 individual scores (Flint et al. 2000; Flint et al. 2013; van Can et al. 2014):

overall score = (satisfy + fullness + [100 - prospective food consumption] + [100 - hunger]) / 4

Summaries of subscores and overall score of retrospective VAS will be provided by treatment for baseline (Day -3), and 15 visits (weekly from Week 1 through Week 15 [Day 1, Day 8, Day 15, Day 22, Day 29, Day 36, Day 43, Day 50, Day 57, Day 64, Day 71, Day 78, Day 85, Day 92, Day 99], and Week 18 [Day 123, Visit 20]), and change from baseline values. Plots of mean scores and mean changes from baseline over time will be provided by treatment.

Food Craving Inventory

Exploratory PD measures to assess the effect of tirzepatide 15 mg versus placebo for change from baseline through Week 18 in FCI 5 subscores and overall score (all are average of nonmissing measurements):

- subscores
 - o high fats (8):
 - Fried chicken, Gravy, Sausage, Hot dog, Fried fish, Corn bread, Bacon, Steak
 - o sweets (8):
 - Cake, Cinnamon rolls, Ice Cream, Cookies, Chocolate, Donuts, Candy, Brownies
 - o carbohydrates/starches (8):
 - Sandwich bread, Rice, Biscuits, Pasta, Pancakes or waffles, Rolls, Cereal, Baked potato
 - o fast food fats (4):
 - Pizza, French fries, Hamburger, Chips
 - fruits and vegetables (5):
 - Cooked vegetables, Fruit juices, Raw vegetables, Canned fruit, Raw fruit
- overall score: all 33 items

Note: The 33-item FCI-II (White et al. 2002) is used to measure cravings for specific 5 food groups. It is scaled in a frequency format assessing the frequency of cravings for 33 foods over the past month or since the last time the participant completed the questionnaire. All items are scored in the following 5-point Likert scale: 1 = Never, 2 = Rarely, 3 = Sometimes, 4 = Often, and 5 = Always. Greater scores denote higher levels of craving.

Food Preference Questionnaire

Exploratory PD measures to assess the effect of tirzepatide 15 mg versus placebo for change from baseline through Week 18 in FPQ scores:

- 6 food categories in Table GPGU 6.3:
 - high fat high sugar, high fat high complex CHO, high fat low CHO/high protein, low fat high sugar, low fat high complex CHO, low fat low CHO/high protein)
 - o mean rating of food items in each category
- high fat and low fat categories
 - o mean rating of food items in each row of Table GPGU 6.3
- high sugar, high complex CHO, and low CHO/high protein categories
 - o mean rating of food items in each column of Table GPGU 6.3
- fat preference score (FPS)

$$FPS = \frac{mean\ hedonic\ rating\ for\ high\ fat\ foods}{mean\ hedonic\ rating\ for\ low\ fat\ foods} \times 100$$

Values of FPS greater than 100 reflect a higher fat preference, and values less than 100 reflect a lower fat preference.

Note: The Food Preference Questionnaire (FPQ) (Geiselman et al. 1998) assesses preferences for 72 foods in a 2 (high-fat, low-fat) by 3 (high-simple sugar, high-complex carbohydrate, low-carbohydrate/high-protein) matrix, with 12 foods in each cell. The macronutrient self-

selection paradigm is an instrument that has to be updated very frequently because of food availability in the grocery stores. During the updates, in the current version of FPQ used in CRF for this study contains 73 food items (where 13 food items in low fat/high sugar category; Table GPGU 6.3).

Subjects rate each food hedonically on a 9-point Likert scale by rating how much they like each food at this moment, with 1 = dislike extremely, 5 = neutral, neither like nor dislike, and 9 = like extremely, and "don't know, never tasted before". "Don't know, never tasted before" are considered missing. The scores for different food categories and FPS (average of nonmissing measurements) will be calculated for statistical analyses.

Table GPGU 6.3 Categorization of FPQ Food Items

	High-Simple Sugar	High-Complex CHO	Low-CHO/High-Protein
	Chocolate layer cake	Pasta with Alfredo Sauce	American cheese
	Snickers	Crescent rolls	BBQ chicken wings
	Pecan pie	Cream of celery soup	Mozzarella cheese
	Apple spice cake	Pizza rolls	Fried chicken leg
	Vanilla ice cream	Onion rings	Pot roast
High-Fat	M&M peanut candies	Potato sticks	Hamburger patty
Ingn-rat	Mounds coconut candy bar	Tortilla chips	Prime rib
	Cheesecake, plain	Fast-food biscuit	Sirloin steak
	Fudge brownie	Stove-Top stuffing	Fried egg
	Chocolate cupcake w/ choc icing	Cheese straws	Peanut butter
	M&M candies, plain	French fries	Fried catfish fillets
	Chocolate ice cream	Potato salad (mayo type)	Scrambled eggs
	Canned pears	Cream of wheat	Boiled shrimp
	Canned apricots	Pita bread	Fat-free cheddar cheese
	Banana, fresh	Long grain rice	Roasted skinless turkey breast
	Dates, dried	Leeks	Canned shrimp in water
	Prunes, dried	Bagel, plain	Stewed chicken breast
	Popsicle, fruit-flavored	White rice	Fat-free string cheese
Low-Fat	Cantaloupe, fresh	French bread	Turkey breast canned in water
	Apple, raw	Baked potato, plain	Broiled red snapper
	Jelly, any flavor	Corn, whole kernel	Spinach
	Watermelon, fresh	Parsnips, cooked	Ground Turkey
	Honeydew melon, fresh	Sweet potato, baked, plain	Boiled crawfish
	Chocolate pudding	Dill pickle	Roasted skinless chicken breast
	Vanilla pudding		

^{*} Abbreviation: CHO = carbohydrate

The above FCI and FPQ parameters will be analyzed respectively in a manner similar to the secondary PD analysis on body weight using MMRM since FCI and FPQ are scheduled to be measured at baseline (Day -3) and twice postbaseline (Day 50 [Week 8] and Day 123 [Week18]).

- ➤ Independent variables: treatment, time, and treatment-by-time interaction as fixed effects, baseline questionnaire parameter as a covariate, and patient as a random effect
- Response variable: change from baseline in questionnaire parameter

Inferential statistics includes LS means and standard error of each of the FCI and FPQ measure for each treatment (tirzepatide, placebo), and the estimated treatment difference (tirzepatide - placebo), corresponding 2-sided 95% CI, and associated p-value.

6.9.2.3.1. Exploratory Pharmacodynamic Analyses on Subcutaneous Adipose Tissue

Exploratory endpoints are change from baseline to Week 18 in exploratory messenger ribonucleic acid (mRNA) expression, lipidomics, metabolomics, or targeted protein assays of subcutaneous adipose tissue biopsy samples, receptor expression, signal transduction, and metabolic changes in adipose tissue. If statistical analyses on these adipose tissue related parameters are conducted, the analyses will be detailed in a separate document and will not require an amendment to this SAP.

6.10. Safety Analyses

Safety measures include, but not limited to, AEs, treatment-emergent adverse events (TEAEs), serious adverse events (SAEs), adverse events of special interest (AESIs), vital signs, and safety laboratory measures.

Unless specified otherwise, safety analyses will be performed on the safety population and presented by treatment group.

Unless specified otherwise, safety listings will display values/events during all study periods. Listings of AEs, death, SAE may include (but not limited to): subject identification (ID) number, age, sex, race, treatment, dose, Medical Dictionary for Regulatory Activities (MedDRA) System Organ Class (SOC), Preferred Term (PT), and time of onset from the first dose of study drug, duration of the AE, seriousness, severity, relatedness to study drug, action taken, and outcome, as appropriate. Additional safety listings will be provided for safety parameters other than AEs in related sections below.

For safety measurements, summary statistics will be provided by treatment. A summary will be provided for AEs with frequency ≥ 10 patients with such event.

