#### 10.3.1. Safety Analyses

##### 10.3.1.1. Clinical Evaluation of Safety

The incidence of AEs for each treatment will be presented by severity and by association with IP as perceived by the investigator. Adverse events reported to occur prior to study entry will be

distinguished from those reported as new or increased in severity during the study. Each AE will be classified by the most suitable term from the medical regulatory dictionary.

All AEs and SAEs will be reported.

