5.2. Determination of Sample Size

[figure not shown]
Up to 56 subjects are planned to be randomized so that approximately 46 subjects complete the study assuming 15% discontinuation rate. These 56 subjects will be randomized to QW tirzepatide or placebo in a 1:1 ratio. The estimated standard deviation of the change in SMR from baseline is 117 kcal/day (Heilbronn et al. 2006). With an expected treatment difference of 100 kcal/day, this provides at least 80% power for the comparison of tirzepatide versus placebo based on 2 sample t-test using 2-sided test at alpha level of 0.05 for the assessment of the primary endpoint.

Abbreviations: DXA = dual energy X-ray absorptiometry; FCI = Food Craving Inventory; FPQ = Food Preference Questionnaire; QW = once weekly; sMMTT = standardized mixed-meal tolerance test; VAS = visual analog scale.

Figure GPGU.5.1. Illustration of study design for Protocol I8F-MC-GPGU.

Clinical Research Unit Procedures

Abbreviations: DXA = dual energy X-ray absorptiometry; FCI = Food Craving Inventory; FPQ = Food Preference Questionnaire; sMMTT = standardized mixed-meal tolerance test; VAS = visual analog scale.

Figure GPGU.5.2. Illustration of clinical research unit procedures.

6. A Priori Statistical Methods

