6.10.2. Treatment-Emergent Adverse Events

A TEAE is defined as an AE which first occurs post first dose of study drug or which is present prior to first dose of study drug and becomes more severe post first dose. The maximum severity for each AE during the baseline period including ongoing medical history will be used as baseline severity.

Treatment-emergent adverse events will be summarized by treatment, severity, and relationship with study drug.

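### SAP 6.10 sets a 10-patient minimum for summarising adverse events without stating its scope; applied to preferred-term counts, it could leave a 9 versus 0 split out of the by-arm table

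*SAP*

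**What the plan says.** The introduction to SAP Section 6.10, which stands above all the safety subsections, first promises summary statistics by treatment for safety measurements. It then adds: "A summary will be provided for AEs with frequency ≥ 10 patients with such event". It gives no reason for the number, no counting basis (pooled or per arm) and no table to which it applies.

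Three other places bear on it:

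- Protocol 10.3.1.1 has no minimum: "The incidence of AEs for each treatment will be presented by severity and by association with IP". It also says that all AEs and SAEs will be reported.
- SAP 6.10.2 has no minimum either: "Treatment-emergent adverse events will be summarized by treatment, severity, and relationship with study drug". It names neither preferred term nor system organ class.
- SAP Section 8 lists four changes from the protocol analyses: the PD analysis set, the sample size text, the food questionnaire and the compliance definition. A frequency cut-off for adverse events is not among them.

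On trial size, SAP 5.2 states: "Up to 56 subjects are planned to be randomized so that approximately 46 subjects complete the study assuming 15% discontinuation rate", and "These 56 subjects will be randomized to QW tirzepatide or placebo in a 1:1 ratio".

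**The concern.** A cut-off of 10 patients is high for a trial of at most 56. A programmer could follow the SAP to the letter, produce an overall severity-by-relationship table under 6.10.2, and apply the 6.10 rule to counts by term. By-arm counts for moderately common events would then have to be rebuilt from a line listing.

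The sentence can fairly be read as a minimum. SAP 6.10.5.8.1 uses the same number as an explicit condition, summarising liver signs and symptoms by treatment only when 10 or more subjects have such data. SAP 6.2 also requires changes to the statistical analyses to be documented and justified in the SAP, so a threshold that narrows the protocol's promise should have been declared in Section 8.

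At stake is how visible term-level imbalances are in the safety report. No data would be lost.

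**Working it through.** **Trial size.** The documents give no derivation of the 10-patient figure. The only computed figure behind the denominator is the sample size, so that is reproduced first. Inputs from SAP 5.2: SD 117 kcal/day, difference 100 kcal/day, two-sided alpha 0.05, two-sample t-test, about 46 completers (23 per arm).

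- Noncentrality = 100 / (117 × √(2/23)) = 2.90 on 44 degrees of freedom. Power from the noncentral t is 80.9% (82.6% by the normal approximation). The stated 80% or more is reproduced.
- 46 / (1 − 0.15) = 54.1, or 55 rounded up, consistent with the planned 56.
- With 1:1 allocation, 56 gives 28 per arm. The safety population is every randomised subject with at least one dose (SAP 6.1), so up to 28 per arm is the relevant denominator.

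**Size of the threshold.** 10/56 = 17.9% of all subjects. If all ten are in one arm, 10/28 = 35.7% of that arm.

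**Splits that fall below a pooled count of 10.** For k versus 0 with equal arms of 28, the two-sided Fisher p-value is 2 × C(28,k) / C(56,k). For k = 9 this is 2 × 6,906,900 / 7,575,968,400 = 0.0018.

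| Split (28 per arm) | Rates | Fisher p |
|---|---|---|
| 9 vs 0 | 32% vs 0% | 0.0018 |
| 8 vs 0 | 29% vs 0% | 0.0044 |
| 7 vs 0 | 25% vs 0% | 0.010 |
| 6 vs 0 | 21% vs 0% | 0.023 |
| 8 vs 1 | 29% vs 4% | 0.025 |
| 5 vs 0 | 18% vs 0% | 0.051 |

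Every split against zero from 6 to 9 patients reaches p < 0.05 and would still miss the cut-off. The p-values only gauge the size of the imbalance; the plan does not propose testing adverse events.

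**How often a real difference would fall below the cut-off.** The documents give no event rates by term, so the rates here are assumptions. With X ~ Binomial(28, tirzepatide rate) and Y ~ Binomial(28, placebo rate), the probability that X + Y ≤ 9 is:

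| Tirzepatide rate | Placebo 0% | Placebo 5% | Placebo 10% |
|---|---|---|---|
| 25% | 0.86 | 0.68 | 0.47 |
| 30% | 0.68 | 0.47 | 0.29 |

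The probability falls quickly for commoner events: 0.14 at 40% versus 5%, and 0.07 at 40% versus 10%.

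**Per-arm count.** If the rule needs 10 patients within at least one arm, the relevant probability is P(X ≤ 9) × P(Y ≤ 9). That is 0.86 at 25% and 0.68 at 30% for all three placebo rates, so more events would be dropped than under a pooled count.

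**The case against.** The sentence does not contain the word only. It says that a summary will be given for adverse events at or above the threshold, not that others will go without one, and the sentence before it promises summaries by treatment with no minimum. SAP 6.10 names adverse events and treatment-emergent adverse events as separate measures, and the threshold mentions only the former. A specific section normally prevails over a general introduction, so 6.10.2 can be read as a by-arm summary free of any cut-off. It also gives the same breakdown as protocol 10.3.1.1, in which case Section 8 had nothing to declare.

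Other outputs limit the harm. SAP 6.10.1 lists all adverse events. SAEs, AEs leading to discontinuation and AESIs have their own listings in 6.10.3 to 6.10.5, and hypoglycemia has its own by-treatment summary and incidence in 6.10.5.1. With at most 56 subjects, a listing can be reviewed by eye.

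Much of this stands. A reader might infer that the SAP bars any event in fewer than 10 patients from every by-arm table. The text does not support that: 6.10.2 commits to a by-treatment summary with no minimum, and nothing says the general rule overrides it. A reader might also infer that such events go unreported, but the listing covers them.

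The objection does not settle the preferred-term table. Section 6.10.2 neither promises one nor exempts itself from 6.10, and the parallel wording in 6.10.5.8.1 keeps the minimum-count reading open.

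**Conclusion.** The point holds as an unresolved and undeclared threshold whose effect depends on how it is applied. The documents do not establish that strongly imbalanced events will be left out. They do allow it, because no section guarantees by-arm counts by preferred term below 10 patients.

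The figures above are therefore conditional on the rule being applied to preferred-term counts. They also assume 56 subjects split 28 and 28, all dosed. The falling-below probabilities rest on assumed event rates and move substantially with the placebo rate, so the range should be read rather than any one value.

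The priority is low: safety and tolerability is an exploratory objective, and the individual events remain in the listing. The change is still worth making, because it improves what the safety report shows at almost no cost.

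**What to change.** In SAP 6.10, delete the 10-patient sentence for adverse events. In SAP 6.10.2, state that all treatment-emergent adverse events will be tabulated by preferred term and treatment arm (n and %), with no minimum frequency.

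If the sponsor wants to keep a cut-off for some additional display, the SAP should name that display, say whether the count is pooled or per arm, give the reason, and record it in Section 8.

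The cost is a longer table. No new data are needed.

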6.10.1. Adverse Events

A listing of adverse events for safety population will be provided, which includes MedDRA PT.

6.10.2. Treatment-Emergent Adverse Events

A TEAE is defined as an AE which first occurs post first dose of study drug or which is present prior to first dose of study drug and becomes more severe post first dose. The maximum severity for each AE during the baseline period including ongoing medical history will be used as baseline severity.

Treatment-emergent adverse events will be summarized by treatment, severity, and relationship with study drug.

6.10.3. Serious Adverse Events

A listing of subjects with SAEs (including death) will be provided.

6.10.4. Adverse Events Leading to Discontinuation

A listing of subjects with AEs leading to discontinuation from study will be provided.

6.10.5. Special Safety Topics

A listing of subjects with all AESIs defined in Section 6.10.5 will be provided.

6.10.5.1. Hypoglycemia

A listing of clinically significant hypoglycemia (plasma glucose <54 mg/dL) and severe hypoglycemia events will be provided. A listing of subjects with hypoglycemic events will be provided. The category of hypoglycemic events (see Table GPGU.6.4 for details) will be presented. A summary will be provided by treatment. The incidence of hypoglycemia will be reported.

Severe/serious hypoglycemia is considered an AESI in this trial.

Table GPGU.6.4. Definitions of Hypoglycemic Event Categories

	Symptoms and/or Signs of Hypoglycemia	Plasma Glucose Level
Glucose alert value	Yes/No/Unknown	
Documented symptomatic hypoglycemia	Yes	∠70 m ≈/dT (2.0 mm ≈1/T)
Documented asymptomatic hypoglycemia	No	≤70 mg/dL (3.9 mmol/L)
Documented unspecified hypoglycemia	Unknown	
Clinically significant hypoglycemia	Yes/No/Unknown	
Documented symptomatic hypoglycemia	Yes	<54 mg/dI (2.0 mmg1/I)
Documented asymptomatic hypoglycemia No		<54 mg/dL (3.0 mmol/L)
Documented unspecified hypoglycemia	Unknown	

Severe hypoglycemia: defined as an episode with severe cognitive impairment requiring the assistance of another person to actively administer carbohydrate, glucagon, or other resuscitative actions. Severe hypoglycemia will be reported as an SAE.

Nocturnal hypoglycemia: defined as any hypoglycemic event that occurs between bedtime and waking.

To avoid duplicate reporting, all consecutive glucose values \leq 70 mg/dL (3.9 mmol/L) occurring within a 1-hour period may be considered to be a single hypoglycemic event.

6.10.5.2. Pancreatitis

A listing of subjects with pancreatitis (including investigator-reported and adjudicated) will be provided. Adjudication assessment results will be reported in the listing.

Treatment-emergent adjudicated-confirmed pancreatitis will be considered as AESI.

6.10.5.3. Thyroid Malignancies and C-Cell Hyperplasia

A listing of subjects with thyroid malignancies and C-cell hyperplasia (search criteria provided in Appendix 1) will be provided.

Thyroid malignancies and C-cell hyperplasia will be considered as AESIs.

6.10.5.4. Major Adverse Cardiovascular Events

A listing of subjects with MACE (including investigator-reported and adjudicated) will be provided. Adjudication assessment results will be reported in the listing.

Only positively adjudicated MACE will be considered as an AESI.

6.10.5.5. Arrhythmias and Cardiac Conduction Disorders

A listing of subjects with arrhythmias and cardiac conduction disorders (search criteria provided in Appendix 1) will be provided.

Severe/serious treatment-emergent arrhythmias and cardiac conduction disorders will be considered as AESI. The cardiovascular events will include clinically relevant rhythm and conduction disorders.

6.10.5.6. Hypersensitivity Events

A listing of subjects with hypersensitivity reactions (search criteria provided in Appendix 1) will be provided.

Only serious/severe cases of hypersensitivity will be considered as AESIs.

6.10.5.7. Injection-Site Reactions

Injection-site assessments for local tolerability will be conducted, when reported as an AE from a patient, or a clinical observation from an investigator.

A listing of subjects with reported injection-site reactions (eg, edema, erythema, induration, itching, and pain) will be provided. Detailed search criteria can be found in Appendix 1.

Only the severe/serious injection site reactions (eg, abscess, cellulitis, erythema, hematomas/hemorrhage, exfoliation/necrosis, pain, subcutaneous nodules, swelling, indurating, inflammation) will be considered as AESIs.

6.10.5.8. Hepatobiliary Disorders

A listing of subjects with events of biliary colic, cholecystitis, or other suspected events related to gallbladder disease will be provided. Detailed search criteria can be found in Appendix 1.

Severe/serious hepatobiliary disorders will be considered as AESIs.

6.10.5.8.1. Hepatic Monitoring

The subjects' liver disease history and associated person liver disease history data will be listed. Concomitant medications acetaminophen/paracetamol, which have potential to cause hepatotoxicity, will be listed. Results from any hepatic monitoring procedures, such as a

magnetic resonance elastography (MRE) scan, and biopsy assessments will be listed, if performed.

Hepatic risk factor assessment data will be listed. Liver related signs and symptoms data will be listed, and it will be summarized by treatment if ≥ 10 subjects with such data. Alcohol and recreational drug use data may be listed.

All hepatic chemistry, hematology, coagulation, and serology data will be listed. Values outside the reference ranges will be flagged on the individual subject data listings.

6.10.5.9. Severe/Serious Gastrointestinal Adverse Events

A listing of subjects with severe/serious gastrointestinal AEs, such as nausea, vomiting, and diarrhea will be provided.

Only the PTs in the gastrointestinal MedDRA SOC with serious/severe cases will be considered as AESIs.

